**Table 2: Schedule of Assessments**

Study Visit	Screening		Predose Assessment		Treatment Period 1		Washout	Predose Assessment		Treatment Period 2		Follow-up
	Admin.	Clinical	TP1, D-2	TP1, D-1	TP1, D1	TP1, D2	W a,b	TP2, D-2	TP2, D-1	TP2, D1	TP2, D2	FU
Study Relative Day/ Study Procedures	-120 to -03	-28 to -03	-2	-1	1	2		-2	-1	1	2	Follow-up c

be kept in cold conditions (~4°C) and returned to the CRC upon collection, as per the instructions provided by the site.

q A 24-hour urine sample should be collected and provided to the site anytime during the Clinical Screening Period, but provision of the sample should be no later than check-in to the CRC at Period 1, Day -2.

r Adverse events to be collected from time of informed consent. This includes the period of an administrative screen, if utilized.

s Applies to subjects assigned to Treatment A, Treatment B and Treatment C only.

t Supplemental oral calcium and active vitamin D will be withheld starting on day of dosing, and through the end of Day 1. Subjects will then resume their usual supplemental oral calcium and active vitamin D at their next usual daily schedule on Day 2.

u Applies to subjects assigned to Treatment D, Treatment E and Treatment F only.

v Supplemental oral calcium should be taken according to the subject's usual daily regimen (but active vitamin D must be withheld).

HBsAg=hepatitis B surface antigen; HCV=hepatitis C virus; HIV=human immunodeficiency virus

**Table 2: Detailed Schedule of Assessments: Day -1 (Prior to Treatment Periods 1 and 2)**

Study Day	-1																		1
Time point (relative to scheduled dosing time on Day 1 [QD, 1st dose BID]) (hour)	Pre-dose	1	1.5	2	3	4	6	8	10	12	13	13.5	14	15	16	18	20	22	24
Vital signs (blood pressure, pulse) a, b	X c	X		X		X	X	X	X	X	X		X		X	X	X	X	X d
ECG (12-lead) a, e	X c	X		X		X	X	X	X	X	X		X		X	X	X	X	X d
IP administration																			X d
PK blood sampling																			X d
PD blood sampling f	X c		X			X	X	X	X	X		X			X				X d
PD urine sampling g, h	X i	→	→	→	→	→	→	→	→	→	→	→	→	→	→	→	→	→	X d

a An attempt to perform these assessments and procedures should be made for any subject who withdraws or is removed from the study.

b Vital signs should be collected in the supine position at each time point. Subject should also be supine at least 5 minutes prior to vitals collection. Vital signs include blood pressure and pulse.

c These assessments should be performed within 30 minutes prior to the relative time of scheduled administration of IP on Day 1.

d Refer to Detailed Schedule of Assessments (Table 3 and Table 4) for collection time points (note: this time point is the same as the pre-dose collection time point on Day 1).

e ECGs will be performed in triplicate measurement at each time point.

f PD blood sampling assessments will include: total serum calcium, magnesium, phosphate, albumin, creatinine, 1,25-dihydroxyvitamin D, and FGF23.

g 24- hour urine collection for PD analysis will be collected according to the following collection intervals (relative to the Day 1 morning dose): pre-dose, 0-3 hours, 3-6 hours, 6-9 hours, 9-12 hours, 12-15 hours, 15-18 hours, 18-24 hours. ‘X’ denotes the start and stop of the entire urine collection period and ‘→’ denotes continuous collection.

h PD urine collection assessments will include: calcium, sodium, citrate, phosphate, magnesium, cAMP and creatinine.

i The predose timepoint for PD urine sampling is used to signify the action that the subject needs to empty his/her bladder immediately before the start of the 0-3 urine collection based on the predicted dosing time of Day 1. It is not a separate pre-dose urine collection.

Table 3: Detailed Schedule of Assessments: Treatment Periods 1 and 2, Day 1/Day 2 (QD Regimen)																						
Study Day	1																				2	
Time point (relative to dosing time on Day 1) (h=hour/m=minute)	Pre-dose	0	10m	20m	30m	1	1.5	2	4	6	8	10	12	13	13.5	14	16	18	20	22	24	
Vital signs (blood pressure, pulse) a, b	X c					X		X	X	X	X	X	X	X		X	X	X	X	X	X	X j
ECG (12-lead) a, d	X c					X		X	X	X	X	X	X	X		X	X	X	X	X	X	X j
Randomization	X e																					
IP administration		X																				
PK blood sampling	X c		X	X	X	X	X	X	X		X		X				X					X
PD blood sampling f	X c						X		X	X	X	X	X		X		X		X			X
Anti-PTH antibody sampling g	X c																					
PD urine sampling h, i	X k	→	→	→	→	→	→	→	→	→	→	→	→	→	→	→	→	→	→	→	→	X

a An attempt to perform these assessments and procedures should be made for any subject who withdraws or is removed from the study.

b Vital signs should be collected in the supine position at each time point. Subject should also be supine at least 5 minutes prior to vitals collection. Vital signs include blood pressure and pulse.

c These assessments should be performed within 30 minutes prior to the scheduled time for IP dose administration on Day 1.

d ECGs will be performed in triplicate measurement at each time point.

e Randomization will occur prior to administration of IP of Treatment Period 1, Day 1 only (and only after all eligibility criteria have been confirmed/re-confirmed).

f PD blood sampling assessments will include: total serum calcium, magnesium, phosphate, albumin, creatinine, 1,25-dihydroxyvitamin D, and FGF23.

g The anti-PTH antibody sample should only be collected at Treatment Period 1, pre-dose (regardless of BID or QD regimen), and the sample collected within 30 mins prior to dosing.

h 24- hour urine collection for PD analysis will be collected according to the following collection intervals: 0-3 hours, 3-6 hours, 6-9 hours, 9-12 hours, 12-15 hours, 15-18 hours, 18-24 hours. ‘X’ denotes the start and stop of the entire urine collection period and ‘→’ denotes continuous collection.

i PD urine collection assessments will include: calcium, sodium, citrate, phosphate, magnesium, cAMP and creatinine.

j The last scheduled serial timepoint (i.e., 24 hours) will also serve as the discharge procedure for these assessments on Day 2.

k The urine sampling under pre-dose in this table is to signify the stop of Day -1, 18-24 hour PD urine collection period, and the start of the Day 1, 0-3 hour PD urine collection period. It is not a separate pre-dose collection.

**Table 4: Detailed Schedule of Assessments: Treatment Periods 1 and 2, Day 1/Day 2 (BID Regimen)**

Study Day	1																					2							
Time point (relative to first dosing time on Day 1) (h=hour/m=minute)	Pre- dose	0	10m	20m	30m	1	1.5	2	4	6	8	10	Pre- dose (12hr)	12	12h 10m	12h 20m	12.5	13	13.5	14	16	18	20	22	24	28	32	36	
Vital signs (blood pressure, pulse) a, b	X c					X		X	X	X	X	X	X c					X		X	X	X	X	X	X	X	X	X	X k
ECG (12-lead) a, d	X c					X		X	X	X	X	X	X c					X		X	X	X	X	X	X	X	X	X	X k
Randomization	X e																												
IP administration		X												X															
PK blood sampling	X c		X	X	X	X	X	X	X		X		X f		X	X	X	X	X	X	X		X		X	X		X	
PD blood sampling g	X c						X		X	X	X	X	X f						X		X	X	X	X	X	X		X	
Anti-PTH antibody sampling h	X c																												
PD urine sampling i, j	X l	→	→	→	→	→	→	→	→	→	→	→	→	→	→	→	→	→	→	→	→	→	→	→	→	→	→	→	X

a An attempt to perform these assessments and procedures should be made for any subject who withdraws or is removed from the study.  
b Vital signs should be collected in the supine position at each time point. Subject should also be supine at least 5 minutes prior to vitals collection. Vital signs include blood pressure and pulse.  
c These assessments should be performed within 30 minutes prior to the scheduled time for IP dose administration on Day 1.  
d ECGs will be performed in triplicate measurement at each time point.  
e Randomization will occur prior to administration of IP of Treatment Period 1, Day 1 only (and only after all eligibility criteria have been confirmed/re-confirmed).  
f Pre-dose PK/PD collection for the second dose of the BID regimen should be completed within 15 minutes prior to the dose.  
g PD blood sampling assessments will include: total serum calcium, magnesium, phosphate, albumin, creatinine, 1,25-dihydroxyvitamin D, and FGF23.  
h The anti-PTH antibody sample should only be collected at Treatment Period 1, pre-dose (regardless of BID or QD regimen), and the sample collected within 30 mins prior to dosing.

**Table 4: Detailed Schedule of Assessments: Treatment Periods 1 and 2, Day 1/Day 2 (BID Regimen)**

Study Day	1																						2					
Time point (relative to first dosing time on Day 1) (h=hour/m=minute)	Pre- dose	0	10m	20m	30m	1	1.5	2	4	6	8	10	Pre- dose (12hr)	12	12h 10m	12h 20m	12.5	13	13.5	14	16	18	20	22	24	28	32	36

i 36- hour urine collection for PD analysis will be collected according to the following collection intervals: 0-3 hours, 3-6 hours, 6-9 hours, 9-12 hours, 12-15 hours, 15-18 hours, 18-24 hours, 24-30 hours, 30-36 hours. ‘X’ denotes the start and stop of the entire urine collection period and ‘→’ denotes continuous collection.

j PD urine collection assessments will include: calcium, sodium, citrate, phosphate, magnesium, cAMP and creatinine.

k The last scheduled serial timepoint (i.e., 36 hour timepoint) will also serve as the discharge procedure for these assessments on Day 2.

l The urine sampling under pre-dose in this table is to signify the stop of Day -1, 18-24 hour PD urine collection period, and the start of the Day 1, 0-3 hour PD urine collection period. It is not a separate pre-dose collection.

## **2.5 Determination of Sample Size**

At least 8 subjects will be required to complete each treatment in each cohort. The sample size was determined based on a similar, prior pharmacokinetic/pharmacodynamic study. The number of subjects in this study is not based on statistical power considerations because the statistical analyses are primarily descriptive, and no hypothesis testing is specified in the study.

## **2.6 Multiplicity Adjustments for Type I Error Control**

Not applicable, as the statistical analyses are primarily descriptive with no hypothesis testing.

### **3. OBJECTIVES**

#### **3.1 Primary Objectives**

To assess the pharmacokinetic profile and pharmacodynamic effects (control of serum calcium and urinary calcium excretion) of rhPTH(1-84) administered as SC doses of 25µg administered twice-daily, 50µg administered twice-daily, and 100µg administered once-daily, as well as the effect of supplemental oral calcium intake, in subjects with hypoparathyroidism.

#### **3.2 Secondary Objectives**

To assess the safety and tolerability of rhPTH(1-84) administration in subjects with hypoparathyroidism.

## **4. SUBJECT POPULATION SETS**

### **4.1 Screened Set**

The Screened Set will consist of all subjects who have signed informed consent.

### **4.2 All-Enrolled Set**

The All-Enrolled Set consists of all subjects who sign the informed consent form and are randomized in the study.

### **4.3 Safety Analysis Set**

The Safety Analysis Set includes enrolled subjects who have received at least 1 dose of rhPTH(1-84). All analyses of safety data will be based on this population.

### **4.4 Pharmacokinetic Set**

The Pharmacokinetic Analysis Set consists of all enrolled subjects who do not have major protocol violations that affect the validity of the PK results, receive at least 1 dose of rhPTH(1-84) and have at least 1 evaluable post-dose pharmacokinetic concentration value available for 1 dose regimen. Subjects who do not meet the inclusion criterion for hypoparathyroidism will be excluded from the PK set. A listing of subjects excluded from the PK Set along with the reason for exclusion is to be generated. In the event of dosing error, proven or suspected based on PK data (extremely low post-dose PTH concentrations), PK data from the subject for the specific treatment period will be excluded from summary tables and figures. A listing of excluded PK data along with reason for exclusion will be generated.

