On Day 1 of Treatment Period 2, subjects will receive the alternative treatment (according to the randomization schedule), following a washout period (≥5 days [ie, 120 hours] and ≤30 days) between administration of the dose or first dose ([for once-daily or twice-daily dosing,

respectively] of each treatment period). All investigational products will be administered via SC injection into alternating thighs at each administration.

At each treatment period, subjects will report to the CRC on Day-2, remain in the CRC through Day 2, and be discharged following the last scheduled assessment on Day 2 (investigators may elect, at their discretion, to keep the subject in-clinic after Treatment Period 1 for the duration of the washout period, eg, if the washout period is short [eg, 120-172 hours] or there are any safety concerns).

For once-daily treatments (Treatments B and E), subjects will receive a single subcutaneous dose of rhPTH(1-84) in the morning on Day 1. For twice-daily treatments (Treatments A, C, D, and F), subjects will receive a subcutaneous dose of rhPTH(1-84) in the morning followed by the second dose 12 hours later on Day 1 (in the opposite thigh). If randomized to rhPTH(1-84) with calcium, subjects will take their supplemental oral calcium within 30 minutes prior to first dose administration. Prior to discharge from the CRC at each treatment period, subjects will be given specific instructions for when to resume taking their supplemental oral calcium and active vitamin D supplements during the day(s) when subjects are not in the CRC.

Subjects enrolled in the study must require daily doses of calcium supplements of  $\geq 1000$  mg prior to baseline (Day 1). Subjects enrolled in the study must also require minimum daily doses of active vitamin D of  $\geq 0.25\mu\text{g}$  (ie,  $0.25\mu\text{g}$  calcitriol or equivalent). Subjects will be expected to adhere to standard meals provided during their confinement in the CRC during each period (from check-in on Day -2 until discharge on Day 2). All subjects (in all treatments) will take their usual doses of supplemental oral calcium and active vitamin D on Day -2 and Day -1.

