### **4.5 Pharmacodynamic Set**

The Pharmacodynamic Analysis Set consists of all enrolled subjects who do not have major protocol violations that affect the validity of the PD results, receive at least 1 dose of rhPTH(1-84) and have at least 1 evaluable post-dose pharmacodynamic value available for 1 dose regimen. Subjects who do not meet the inclusion criterion for hypoparathyroidism will be excluded from the PD set. A listing of subjects excluded from the PD Set along with the reason for exclusion is to be generated. In the event of dosing error, proven or suspected based on PK data (extremely low post-dose PTH concentrations), PD data from the subject for the specific treatment period will be excluded. During treatments A, B, and C, if a subject takes supplemental oral calcium/active vitamin D within 24 hours post the last rhPTH(1-84) dose, PD data from the subject for the specific treatment period will be excluded from summary tables and figures. A listing of excluded PD data along with the reason for exclusion will be generated.

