### **12.3 Pharmacokinetic Methods**

All summaries and analyses of the pharmacokinetic data will be based on the Pharmacokinetic Set. After database lock, a visual inspection of concentration-time profiles and pharmacokinetic parameters will be performed by PRA to determine dataset integrity and potential outliers. Descriptive statistics of pharmacokinetic parameters may be calculated with and without subjects with potential outlier data. Subjects with potential outlier data will be reviewed by Shire for inclusion/exclusion from the descriptive statistics on a case-by-case basis.

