#### **12.3.2 Baseline-adjusted PTH Concentration Data**

Baseline-adjusted PTH concentrations (subject- and period-specific) are to be calculated by subtracting baseline endogenous PTH from the raw PTH concentrations. The baseline is defined as pre-morning-dose endogenous PTH level on Day 1 for each treatment period. Since rhPTH(1-84) is administered to subjects with hypoparathyroidism in this study, baseline endogenous PTH levels are expected to be low and likely below the lower limit of quantification (LLOQ) for PTH. If the baseline-adjusted PTH concentration gives a negative value then the baseline-adjusted PTH concentration should be set to zero. In the terminal phase (after the morning dose during the QD treatment and after the evening dose during the BID treatment), any positive baseline-adjusted PTH concentrations following a negative value will be assigned a value of zero.

If the pre-dose PTH value is missing, then this is set to 0 for the calculation of the baseline-adjusted PTH concentration for the purposes of calculating the baseline-adjusted pharmacokinetic parameters.

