#### **12.3.3 Pharmacokinetic Parameters**

The pharmacokinetic analysis will be conducted by using WinNonlin Phoenix version 6.3 or higher (Pharsight Corporation, Mountain View, California, USA). Pharmacokinetic

parameters will be determined from the plasma PTH concentration-time data by non-compartmental analysis. Pharmacokinetic analyses based on raw and baseline adjusted PTH concentrations will be performed. In each treatment period, all assessment dates will be related to the first day of rhPTH administration. This first day of investigational product administration is referred to as Day 1. Day-1 is the day that is preceding Day 1, and a Day 0 will not be defined.

The pharmacokinetic parameters will include, but may not be limited to:

- Time of maximum observed concentration sampled during a dosing interval ( $t_{max}$ ), to be reported in the unit of hour (original and baseline-adjusted)
- Maximum observed concentration ( $C_{max}$ ), to be reported in the unit of pg/mL (original and baseline-adjusted)
- Area under the curve from the time of dosing to the last measurable concentration ( $AUC_{last}$ ). Calculated using the linear up/log down method, to be reported in the unit of pg.hr/mL (original and baseline-adjusted)
- Area under the curve extrapolated to infinity calculated as  $AUC_{last} + C_{last}/\lambda_z$  ( $AUC_{0-inf}$ ). Calculated using the linear up/log down method, to be reported in the unit of pg.hr/mL (baseline-adjusted only)
- % of AUC extrapolated from the last measurable concentration to infinity over  $AUC_{(0-inf)}$  (%AUC extrapolated) (baseline-adjusted only)
- Area under the concentration curve from time zero to 24 hours post the first dose ( $AUC_{0-24h}$ ), to be reported in the unit of pg.hr/mL (calculated using the linear up/log down method) (original and baseline-adjusted)
- Area under the concentration curve from time zero to 12 hours post the first dose ( $AUC_{0-12h}$ ) calculated using the linear up/log down method, to be reported in the unit of pg.hr/mL (for BID treatment only, original and baseline-adjusted)
- Area under the concentration curve from the time of the second dose to 12 hours post the second dose ( $AUC_{12-24h}$ ) calculated using the linear up/log down method, to be reported in the unit of pg.hr/mL (for BID treatment only, original and baseline-adjusted)
- Elimination rate constant associated with the terminal (log-linear) portion of the curve ( $\lambda_z$ ) (baseline-adjusted only)

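### Periods dropped on suspicion alone, because post-dose PTH is very low, should be summarised both with and without that period; the SAP commits to only one version

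*SAP*

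**What the plan says.** The PK and PD profiles are the primary objective (SAP 3.1). The study is open-label (SAP 2.3) and descriptive, with no hypothesis testing (SAP 2.5).

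- **SAP 4.4 (PK set):** "In the event of dosing error, proven or suspected based on PK data (extremely low post-dose PTH concentrations), PK data from the subject" for that treatment period leave the summary tables and figures. A listing of excluded data with reasons is required.
- **SAP 4.5 (PD set):** "In the event of dosing error, proven or suspected based on PK data (extremely low post-dose PTH concentrations), PD data from the subject" for that treatment period are excluded. This sentence does not repeat the limit to summary tables and figures. A listing with reasons is again required.
- **SAP 12.3:** "Descriptive statistics of pharmacokinetic parameters may be calculated with and without subjects with potential outlier data". SAP 12.4 says the same for PD parameters. In both, the review follows database lock and inclusion is decided case by case.
- **Protocol 9.7** defines the PK and PD populations only by at least one dose and at least one evaluable post-dose value. **Protocol 9.4** leaves the handling of missing, unused and spurious data to the SAP.
- **Protocol 6.5** requires dosing to be observed, and the CRF captures time, date and dose level.
- **SAP 17** declares no change from the protocol's planned analysis.

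**The concern.** The dosing-error sentence has two branches. The proven branch rests on evidence independent of the result. The suspected branch rests on the PTH result itself, which is an outcome the study exists to describe. It acts on low values only, so if it removes a genuine low exposure it can only raise the exposure summaries and narrow their spread. The same decision takes out that subject's calcium and urine data for the period. Nothing keeps the judgement blind to treatment, and SAP 4.4 and 4.5 do not say who makes it or when.

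The opposite error also exists. Dosing records may not reveal an injection that was given on time but not delivered, and keeping such a period pulls exposure down. In a descriptive study the summary tables are the result, so which version is printed matters. The plan commits to one version and leaves the choice to judgement after the data are seen.

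**Working it through.** The plan has no power-based figure to reproduce. The planned size is 4 cohorts × 8 = 32, as stated. The documents give no CV for PTH exposure and no numerical meaning for extremely low. Both are therefore assumed: lognormal exposure with CV 30/50/70%, and a main reading of below 20% of the treatment's observed median. That reading is plausible because SAP 12.3.2 says "baseline endogenous PTH levels are expected to be low and likely below the lower limit of quantification (LLOQ) for PTH", so a failed dose should sit near baseline.

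**Step 1. Log-scale SD.** σ = √ln(1+CV²) = 0.294 / 0.472 / 0.631.

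**Step 2. Chance of a false exclusion.** All 8 subjects are correctly dosed, and any value below the stated fraction of the observed median is dropped. Simulation (400,000 trials per case):

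| Reading | n | CV 30% | CV 50% | CV 70% |
|---|---|---|---|---|
| below 20% | 8 | 0% | 0.4% | 5% |
| below 33% | 8 | 0.1% | 8% | 27% |
| below 50% | 8 | 8% | 43% | 67% |
| below 20% | 16 | 0% | 0.7% | 9% |

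Hand check with the true median, 1 − (1 − Φ(ln 0.20/σ))⁸: 0 / 0.26 / 4.2%. The observed median varies from sample to sample, so the simulated values are slightly higher. The 33% and 50% readings are looser than the text suggests.

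**Step 3. Size when it happens.** If the dropped value is a fraction r of the geometric mean of the other seven, the geometric mean rises by the factor r^(−1/8). At r = 0.20 this is 0.20^(−1/8) = 1.22, and lower values give more. In the simulated n=8 trials with a false exclusion under the 20% reading, the average rise is about 25% at CV 50% and 28% at CV 70%. At CV 30% no trial had one.

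Averaged over all trials, the n=8 shift is only 0 / +0.1 / +1.3%.

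**Step 4. The opposite error.** A once-daily dose delivered at 10% and kept multiplies the geometric mean by 0.1^(1/n):
- n = 8: 0.1^(1/8) = 0.75, a fall of 25%.
- n = 16 (B or E pooled over two cohorts): 0.1^(1/16) = 0.87, a fall of 13%.

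**Step 5. PD.** One period is 1/8 = 12.5% of the weight in an n=8 mean. The documents give no variance for the PD parameters in these regimens, so no shift is computed.

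**Step 6. What is committed.** The excluded data are listed. No section requires a second summary when a period is excluded for a suspected dosing error.

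**The case against.** The best defence is that exclusion of this kind is allowed and visible. Protocol 9.4 delegates spurious data to the SAP. Excluded data are listed with reasons (Listing 5.11). The outlier clause already permits with/without statistics, and a very low profile could qualify. On the plausible reading the average bias is negligible, and the 25% fall from keeping a failed dose supports having an exclusion rule. All of this stands. What it does not supply is the second summary: a listing of exclusions is not one, and a permission is not a commitment.

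Several stronger readings are tempting and are not supported:

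- **That the rule biases exposure upwards to a material degree.** On the 20% reading the average shift is at most +1.3%. The harm is conditional on a false exclusion.
- **That the SAP names no basis for the judgement.** It names post-dose PTH concentrations; what is missing is a cut-off.
- **That twice-daily periods have no rule.** SAP 2.1 gives them two injections ("For twice-daily treatments (Treatments A, C, D, and F), subjects will receive a subcutaneous dose of rhPTH(1-84) in the morning", then a second dose 12 hours later), but SAP 4.4 read literally drops the whole period for any dosing error. That is blunt, not absent.
- **That a failed twice-daily injection would slip through because AUC0-24h stays high.** The SAP does not use an AUC rule, and it samples PTH densely after the second dose.
- **That no paired table is planned, because SAP Section 20 lists none.** This is weak evidence: SAP 1 places output specifications in a separate document.

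**Conclusion.** The point holds as a gap in commitment, not as a forbidden exclusion. The suspected branch of SAP 4.4 and 4.5 selects on a primary outcome in one direction, and the plan promises only one of the two summaries a reader needs. Under the assumed CVs and the 20% reading, wrongful exclusion is unlikely (0/0.4/5% per 8 subjects) but raises the geometric mean by about 25–28% when it occurs. Keeping a once-daily dose delivered at 10% lowers it by about 25% (n=8) or 13% (n=16). The textual gap is certain; the sizes depend on the assumptions. No type I error or power is at stake, because nothing is tested.

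Three clarifications are secondary, and the point does not depend on them: the twice-daily case, the differing exclusion wording in 4.4 and 4.5, and SAP 17. On the last, four exclusions are absent from Protocol 9.7:
1. major protocol violations;
2. the hypoparathyroidism criterion ("Subjects who do not meet the inclusion criterion for hypoparathyroidism will be excluded from the PK set", and likewise for PD);
3. proven or suspected dosing error;
4. for PD only, supplement intake ("During treatments A, B, and C, if a subject takes supplemental oral calcium/active vitamin D within 24 hours post the last" dose).

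A reader might infer that these additions were improper. Protocol 9.4 gives the SAP room to handle spurious data; what is inaccurate is the statement that nothing changed.

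**What to change.** **Main change (SAP 4.4, 4.5, 12.3, 12.4).** Keep the exclusion of documented dosing errors. For any period excluded only on suspicion from PK data, or as an outlier, require the affected PK and PD parameter summaries both with and without that period, with all other exclusions held the same.

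**Cost.** SAP wording, plus one extra column for the affected treatment, only when a period is excluded. At most 38 of the 57 PK/PD summary tables in SAP Section 20 are parameter tables (4 PK + 14 serum + 20 urine). The version that includes the period may contain a failed injection, so the two columns must be read together.

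**Why not just a cut-off.** A stated cut-off would help, but it would not replace the paired summary. A dose delivered at 25% falls below 20% of the median with probability Φ(ln(0.20/0.25)/σ) = 22/32/36%, so a 20% rule would miss most of them.

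**Secondary clarifications.**
- Say whether one failed twice-daily injection removes the whole period. SAP 12.3.3 already defines a second-injection parameter ("Area under the concentration curve from the time of the second dose to 12 hours post the second dose") if a narrower rule is intended.
- Use the same exclusion wording in 4.4 and 4.5.
- List all four added exclusions in SAP 17.
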